19.4 Case Report Forms (CRFs)

CRFs will be created for each subject participating in the study to ensure consistent data collection. The Investigator or his/her authorized designee must ensure that all information has been accurately entered and that correct dates and required signatures are present.

19.5 Review of Source Records

The Investigator agrees that qualified representatives of the Sponsor and regulatory agencies will have the right, both during and after this study, to conduct inspections and to audit and review medical records pertinent to the clinical study as permitted by the regulations. Subjects will not be identified by name, and confidentiality of information in medical records will be preserved. The confidentiality of the subject will be maintained unless disclosure is required by regulations.

Accordingly, the following statement (or similar statement) will be included in the informed consent document: Representatives of regulatory agencies, IRBs and the sponsor may review your medical records and all information related to this study as permitted by law. Identifying

information will not appear on any record received by the sponsor. Each subject's identity will remain confidential unless disclosure is required by law.

19.6 Monitoring of the Study

Clinical monitoring visits will be scheduled prior to the commencement of the study and at regular intervals thereafter. The Investigator shall cooperate with the study monitor. This includes, but is not limited to, allowing the inspection of facilities utilized by the Investigator for this clinical investigation, providing access to subject medical records for review and verification purposes; providing all required reports; and providing all other reports, including any subject report forms reasonably requested by Neuronetics. The Investigator shall also permit, at reasonable times, an authorized officer or employee of the FDA to inspect the facilities utilized by the Investigator for the clinical investigation. The Investigator will also permit this representative to inspect, copy and verify records required, as part of, or relevant to the investigation.

Clinical monitoring visits will be scheduled in advance to ensure that the Investigator and other appropriate staff have sufficient time available to meet with the monitor and discuss all relevant findings. In addition to regular visits by the monitor, more frequent follow-up visits will be scheduled if the Investigator fails to provide adequate subject data or if otherwise deemed necessary. Subject data will be reviewed and/or verified, and all deficiencies corrected on site, if possible. A complete report will be made of all monitoring visits. If the study is terminated, a monitor will visit the site to ensure that all records are complete, the IRB is notified, and all Neuronetics materials are retrieved.

The monitor will review the study conduct to determine compliance with the study protocol. Protocol deviations are not permitted without prior written approval from Neuronetics and, if necessary, the reviewing IRB and/or FDA. The monitor will review and/or verify all case report forms and source documents as appropriate to ensure that correct and adequate copies are available for the investigational study. The monitor will review the subject informed consent forms to ensure that no forms were signed prior to the date of IRB approval of the study. The monitor will inspect the facilities and equipment used in the investigation to ensure that they are appropriate for use and properly maintained.

The monitor will assess the site to assure the Principal Investigator is properly overseeing the study activities of associate Investigators, if applicable.

19.7 Protocol Amendments

Any significant change in this protocol requires a protocol amendment. The Investigator and the medical monitor will indicate their approval by signing the approval page of the amendment. After sponsor approval of a protocol amendment, the Investigator will submit the amendment to the IRB for written approval. The approval letter must refer specifically to the Investigator, the sponsor protocol number, the protocol title, the protocol amendment number, and the date of the protocol amendment. The Sponsor will submit a copy of the protocol amendment to the appropriate regulatory agency.

A protocol amendment may be implemented following IRB approval. In some cases, an amendment must receive a favorable opinion from the regulatory agency. A protocol change intended to eliminate an apparent immediate hazard to subjects may be implemented immediately, but the change must then be documented in an amendment, reported to the IRB within 5 working days, and submitted to the appropriate regulatory agency in the required time frame.

19.8 Change in Investigator

If any Investigator retires, relocates, or otherwise withdraws from conducting this study, the responsibility for maintaining records may be transferred to the Sponsor, IRB, or other Investigator. The Sponsor must be notified of and agree to the change. Regulatory agencies will be notified with the appropriate documentation.

19.9 Termination by the Sponsor

The sponsor may terminate the study at any time for any of the following reasons:

1. Failure to enrol subjects.
2. Protocol violations.
3. Inaccurate or incomplete data.
4. Unsafe or unethical practices.
5. Questionable safety of the test article.
6. Suspected lack of efficacy of the test article.
7. Administrative decision.

19.10 Termination by the Investigator

If the Investigator terminates the study prematurely, he/she must:

1. Return all investigational devices, CRFs, and related study materials to the Sponsor.
2. Provides the IRB and the sponsor with a written statement describing why the study was terminated prematurely. **Note:** Prompt compliance with this requirement is essential so that the sponsor may comply with its regulatory obligations.

19.11 Final Study Report

The Investigator will complete a report notifying the IRB of the conclusion of the clinical study. This report should be made within 3 months of completion or termination of the study. The final report sent to the IRB will also be sent to Neuronetics and, along with the completed CRFs, will constitute the final summary to Neuronetics, thereby fulfilling the Investigator's regulatory responsibility.

When the Sponsor generates reports for presentations to regulatory agencies, one or more of the Investigators who have contributed significantly to the study will be asked to endorse the final report. The endorsement is required by some regulatory agencies.

19.12 Confidentiality

All unpublished information provided to the Investigator by the Sponsor shall be kept confidential and shall not be published or disclosed to a third party without the prior written consent of the Sponsor.

The Investigator shall not make a patent application based on the results of this study and shall not assist any third party in making such an application without the written authorization of the sponsor unless otherwise specified in the study agreement.

19.13 Publications

The institution and Investigator shall not publish or present data from the study center until the study has been presented in full or for two years after the termination of the study, whichever occurs first. Subsequent publications must refer to the multicenter findings. Thereafter, if the Investigator expects to participate in the publication of data generated from this site, the institution and Investigator shall submit reports, abstracts, manuscripts and/or other presentation materials to the Sponsor for review prior to submission for publication or presentation.

The Sponsor shall have 60 days to respond with any requested revisions, including without limitation, the deletion of confidential information. The principal Investigator shall act in good faith upon requested revisions, except the Investigator shall delete any confidential information from such proposed publication. The Investigator shall delay submission of such publication or

CONFIDENTIAL

presentation materials for up to an additional 90 days in order to have a patent application(s) filed.

19.14 Subject Injury

A study-related injury is a physical injury that is directly caused by the study device or procedures required and described in the study protocol or by medical procedures that are required by the study and that are not standard of care.

Other than questionnaires, there are no study procedures or medical procedures required in this study that are not standard of care so no compensation for study related injury will be provided.

If laws or regulations of the locality in which the trial is taking place require additional payment of expenses, the Sponsor shall comply with such law or regulation. Where applicable, the Sponsor has taken specific national insurance.

19.15 Record Retention

Consistent with federal regulations, Investigators shall retain and preserve one copy of all data generated in the course of the study, specifically including but not limited to those documents defined by GCP as essential documents, for the longer of: (i) 2 years after the last marketing authorization for the investigational device has been approved or the Sponsor has discontinued its research with respect to such device or (ii) such longer period as required by applicable global regulatory requirements. At the end of such period, the Investigator shall notify the Sponsor, in writing, of its intent to destroy all such material. The Sponsor shall have 30 days to respond to the Investigator's notice, and the Sponsor shall have a further opportunity to retain such materials at the sponsor's expense.

20 ATTACHMENTS

Attachment A – Treatment MT Escalation and Tracking Worksheet

Subject ID#	Ramp Phase		Do NOT inform patient of treatment X or Y								
	Start at 90%MT		Determine tolerance at each interval and increase %MT by 10% if Tolerable								
Date	Treatment MT %	% MT Changes For Both Treatment X and Treatment Y									
		Initial Tx		3:45-7:30		7:30-11:15		11:15-15:00		15:00 - 18:45	
Treatment Day		Start	End	Start	End	Start	End	Start	End	Start	End
MT:		60									
		70									
		80									
		90									
	100										
	110										
	120										
		 C.S.  Pref				 C.S.  Pref					
Do NOT Inform Pt. when they are changing % MT dose				First Treatment: Comfort Scale at minute 3:45 and End of Treatment; For all subsequent treatments include preference							

Attachment B – Comfort Visual Analogue Scale: (VAS)

"Mark just ONE spot on the line below that best shows the level of discomfort/pain you may have felt during the treatment, where '0' means you didn't feel any discomfort/pain at all and '100' means you felt extreme discomfort/worst pain you can imagine. Please mark only ONE spot on the line with an X that looks about right for your pain level during treatment. Do not think of or write in a number."

## 1 Introduction

This statistical analysis plan (SAP) describes the planned statistical methods to be used during the reporting and analysis of data and should be read in conjunction with the study protocol and case report forms (CRFs). Any revisions to the protocol or CRFs that impact the planned analyses may require updates to the SAP.

## 2 Abbreviations

Abbreviation/Term	Definition
CRF	Case Report Form(s)
MDD	Major depressive disorder
MT	Motor threshold
rTMS	Repetitive transcranial magnetic stimulation
SAP	Statistical Analysis Plan
SRS	Study Requirement Specification

## 3 Study Objectives

### 3.1 Primary Objective

The Primary objective is to evaluate the comfort associated with TMS treatment when applied with the standard Dash treatment protocol vs. the Dash protocol with the SoftStart feature enabled.

### 3.2 Secondary Objectives

The Secondary objectives are to evaluate the ability to reach the prescribed treatment intensity, the time it takes to reach the prescribed treatment intensity, maximum treatment intensity reached, patient treatment preference and other treatment effects between the two treatment protocols.

### 3.3 Study Endpoints

Primary endpoint: The difference in the change in VAS scores for Comfort after rTMS (repetitive transcranial magnetic stimulation) between treatments administered with the Dash protocol (treatment Y) and treatments administered with the Dash protocol with SoftStart feature enabled (treatment X). Comfort will be evaluated as a change for all observations between groups, observations from Baseline to end of escalation phase, observations between groups during the crossover phase and observations

Statistical Analysis Plan		Page 6 of 18
Sponsor Neuronetics	Study Comfort Start	Version 1.0

within a patient between treatments in the cross-over phase. Comfort will also be analyzed over time and by number of treatments between groups.

After the final study treatment, the treatment protocol planned for remaining TMS sessions, and reason for choosing it, will be documented as a secondary study endpoint and the subject will be exited from the study.

If adverse events occur, those data will be summarized using standard descriptive statistics (frequency distributions, percentages, listings).

## **4 Study Design**

This is a prospective, randomized, single center, single blind study conducted in an adult population being treated for MDD (major depressive disorder).

For each patient, the study will consist of up to approximately 14 days, one hour for screening and 30 minutes during each daily treatment session. The goal of the study is to monitor and compare patient comfort (treatment area sensitivity) using two different treatment protocols at the start of TMS therapy where the stimulation intensity is typically escalated over 1-10 treatments until the patient is comfortable with the prescribed treatment dose (% MT; typically, 120%).

Each subject, of approximately 40, will be treated with rTMS for MDD as diagnosed and prescribed by their treating physician. Following consent and successful study qualification, study subjects will be randomized to the standard Dash protocol or the modified Dash protocol with the SoftStart feature enabled.

Prior to rTMS stimulation, the Motor Threshold (MT) will be established for each subject individually. Total treatment time per day is 18 minutes 45 seconds for either of the two treatments. Every treatment day patients will receive 75 fifteen second cycles. Each cycle is a 40 pulse train of 4 seconds with 11 seconds off (Dash), or a 50 pulse train of 5 seconds with 10 seconds off (Soft Start Dash). The extra 10 pulses per Soft Start Dash train are an eight pulse ramp-up sequence and a two pulse ramp-down sequence.

At the start of the 6th Treatment session or the session after the subject reaches the prescribed dose, the subject will be switched to the alternative treatment protocol and continue to alternate treatment each day for the next 4 treatments.

Each day of these 4 treatment sessions, at end of the first time interval (3:45 min, total of a set of 15 fifteen second cycles) and the end of the session, the subject will complete the comfort/pain questionnaire and be asked whether they preferred the current treatment, or the treatment received at the previous session (Today's Treatment, Last Treatment, No Difference).

Statistical Analysis Plan		Page 7 of 18
Sponsor Neuronetics	Study Comfort Start	Version 1.0

During treatments, the subject will be asked to complete several questionnaires, including comfort/pain, treatment preference, and depression questionnaires.

## **4.1 Randomization**

Subjects will be randomized prior to study start, to the initial treatment received prior to first crossover. Randomization will be performed using random permuted blocks of sizes 2 and 4, stratified by gender, with a 1:1 allocation ratio (Dash protocol / Dash protocol with SoftStart). A single site handling 40 total subjects is planned. Extra subjects and sites will be randomized, in the event unforeseen changes become necessary. Randomized treatment will be assigned by paper envelopes only, no database will be utilized.

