## **5 Sample Size Determination**

A sample size of 40 total subjects, twenty to begin treatment with each of the two study arms, was selected as sufficient to perform a preliminary assessment of the differences between the two repetitive transcranial magnetic stimulation (rTMS) therapies for MDD. The sample size is not based on formal power requirements for a statistical hypothesis test but is based on a desire to obtain a reasonable initial data set for exploratory and planning purposes.

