### **6.6.2 Primary Efficacy Endpoints**

The Primary study outcome assessments will be determined based on differences in the mean VAS ratings on a 0-10cm VAS scale for comfort (the scale ranges from 0-100, and 0 = no pain or discomfort, and 100 = extreme discomfort or worst pain imaginable). Statistical methods employed to detect differences between the experimental and the control groups, for the below outcomes, may include a t-test, Chi-Square test, and Fisher's Exact test. Test for normality and equality of variances may be used for continuous parameters. If data are found to fail one or both, then nonparametric methods may be employed, eg, Wilcoxon Rank Sum test. For assessments including crossovers, a relevant method accounting for period effect, repeated measures, and randomized order may be utilized.

Analyses outlined below will be done for the average of patient scores.

One of the following analyses will be employed as the primary analysis of the primary efficacy endpoint:

Statistical Analysis Plan		Page 11 of 18
Sponsor Neuronetics	Study Comfort Start	Version 1.0

The difference in the change in Visual Analog Scale scores for Comfort after rTMS stimulation between treatments administered with the Dash protocol and with New feature enabled. Comfort will be evaluated as a change for all observations between groups, observations from Baseline to end of escalation phase, observations between groups during the crossover phase and observations within a patient between treatments in the cross-over phase.

At minute 3:45, and at the end of the treatment session, the subject will be asked to complete a Visual Analog Scale (VAS), for Comfort/Pain.

- a. All over group (throughout the whole trial, Ramp phase & Crossover phase) – all VAS scores for X → Y or Y → X (similar to 1.d.ii above. Start with the average of the 3:45, 18:45 scores on each Day for each subject, then average each of the daily X averages and average each of the daily Y averages for each patient, comparing the average of the 40 X averages to the average of the 40 Y averages, a one-sided hypothesis test evaluating if the “with Comfort Start” group, X, has lower average scores)

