- b. Between group comparison: Prior to cross over (reaching 120%MT): combination of the scores at 3:45 min and at the end of treatment, 18:45 min; (start with the average of the these two scores for each subject that reached 120% (average of all scores prior to & including 120%), then compare the average of the X averages (at most 20) to the average of the Y averages (at most 20), a one-sided hypothesis test evaluating if the “with Comfort Start” group, X, has lower average scores)
- a. Average of all the patient scores for all Crossover Phase treatments (start with the average of the 3:45 and 18:45 scores on each Crossover Day for each subject, then average each of the daily X averages and average each of the daily Y averages for each patient, comparing the average of the 40 X averages to the average of the 40 Y averages, a one-sided hypothesis test evaluating if the “with Comfort Start” group, X, has lower average scores)

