## **6.8 Subgroup Analyses**

Subgroup analysis may also be performed based on gender, initial comfort scores, group assignments or other variables. Specifically, an examination may be done to determine if differences between treatment arms are consistent across males and females, to investigate whether females are more sensitive to pain overall, descriptively only, or additionally via one-sided hypothesis tests.

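### Randomisation is stratified by gender, but between-subject comparison (b), a candidate primary analysis, has no gender term, so its reported standard error may be overstated

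*SAP*

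**What the plan says.** SAP 4.1 describes permuted blocks of 2 and 4, "stratified by gender, with a 1:1 allocation ratio". Gender is the only stratification factor.

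SAP 6.6.2 leaves the primary analysis open: "One of the following analyses will be employed as the primary analysis of the primary efficacy endpoint". Of the analyses then listed, (b) is the comparison between subjects. It takes a VAS average "for each subject that reached 120% (average of all scores prior to & including 120" percent, and the instruction is then to "compare the average of the X averages (at most 20) to the average of the Y averages (at most 20"). No covariate is named.

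The tests offered are a t-test, Chi-square and Fisher's exact test. If normality or equal variances fail, "then nonparametric methods may be employed, eg, Wilcoxon Rank Sum test". The only sentence about modelling is limited to assessments that include crossovers: "a relevant method accounting for period effect, repeated measures, and randomized order may be utilized". Gender is not in that list. Protocol 18.2 names the same tests and adds no gender adjustment.

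Elsewhere in the SAP's analysis sections, gender appears only in section 6.8, where "an examination may be done to determine if differences between treatment arms are consistent across males and females". That section also raises, as an open question, whether women are more sensitive to pain.

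On size, SAP 5 says: "The sample size is not based on formal power requirements for a statistical hypothesis test".

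**The concern.** Stratifying by gender keeps the arms close to balanced on gender, so a gender difference in VAS adds almost nothing to the variability of the difference between arms. A plain two-sample test does not know this. It leaves the gender difference in the residual variance and reports a standard error suited to unstratified allocation. The interval is then wider than it needs to be, and the test rejects less often than its nominal level under the null.

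The plan therefore controls a factor in the design and does not use it in the analysis. Comparison (b) has at most 20 subjects per arm and could become the primary analysis. The data set is meant for planning, so the reported interval is one of its main products.

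**Working it through.** The documents state no effect size, SD or power, so there is no figure of the plan's own to reproduce. The check measures the cost of leaving gender out over a range of assumed gender gaps.

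**Inputs from the documents.** 40 subjects, 20 per initial arm (SAP 5). Blocks of 2 and 4 within gender, 1:1 (SAP 4.1). Only subjects reaching 120% MT enter (b) (SAP 6.6.2). Tests of X against Y are one-sided (SAP 6.6.2), with no separate one-sided level given; SAP 6.1.4 sets two-sided 0.05 as the default.

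**Assumptions.** Normal VAS with within-gender SD 1; 60% women; gender gap γ of 0, 0.3, 0.5 or 0.8 SD; for power, a treatment effect of 0.8 SD and a one-sided level of 0.05. The number reaching 120% MT is unknown, so the analysed set is taken as a random 40, about 32 or about 24 of the 40.

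**Step 1, approximation with all 40 analysed.** With p the proportion of women, the variance the unadjusted test sees is 1 + p(1 − p)γ². The gender model sees 1. The ratio of interval widths, unadjusted over adjusted, is about √(1 + 0.24γ²):
- γ = 0: √1 = 1.000
- γ = 0.3: √1.0216 = 1.011
- γ = 0.5: √1.06 = 1.030
- γ = 0.8: √1.1536 = 1.074

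The adjusted model has 37 degrees of freedom instead of 38. The ratio of 97.5% t quantiles is 2.0244/2.0262 = 0.999, which is the cost of about 0.1% at no gap.

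**Step 2, simulation (20,000 trials per setting).** Ratio of 95% interval widths, t-test over linear model with treatment and gender:

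| Analysed | γ = 0 | 0.3 | 0.5 | 0.8 |
|---|---|---|---|---|
| 40 | 0.999 | 1.010 | 1.029 | 1.075 |
| about 32 | 0.994 | 1.006 | 1.025 | 1.070 |
| about 24 | 0.987 | 0.997 | 1.016 | 1.062 |

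The first row agrees with Step 1. Adjustment breaks even at a gap near 0.2 SD with about 32 analysed and near 0.3 SD with about 24.

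**Step 3, what is lost.** With 40 analysed, the true SD of the estimate without and with the gender term is 0.318 and 0.318 at a 0.3 SD gap, 0.322 and 0.322 at 0.5, and 0.316 and 0.315 at 0.8. The estimate itself is equally precise; only its reported standard error differs. The two estimates separate somewhat when the analysed set shrinks and the gap is large: 0.424 and 0.411 with about 24 analysed and a 0.8 SD gap.

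**Step 4, effect on the test with 40 analysed.** At γ = 0, 0.3, 0.5 and 0.8, the one-sided type I error of the t-test (nominal 0.05) is 0.051, 0.051, 0.045 and 0.040. The linear model stays between 0.049 and 0.053. Power, t-test against linear model, is 0.800 and 0.799, 0.798 and 0.803, 0.782 and 0.796, and 0.759 and 0.798.

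**Step 5, the other candidates.** The other two listed analyses start from each patient's own X average and Y average. When the within-patient difference is analysed, a gender main effect cancels, so the point concerns (b) alone.

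**The case against.** The strongest case against the point is that the harm rests on an assumed input. The documents give no gender effect and only raise the possibility of looking for one. At a 0.3 SD gap the gain is 1.0% of width with 40 analysed, and becomes a 0.3% loss with about 24. A gain of 7.5% needs a 0.8 SD gap, for which the documents offer no basis. The test list is permissive, so adjustment is not ruled out. The study is exploratory and has no power target. Comparison (b) may never be chosen as primary, and its restriction to subjects who reach 120% MT is a larger problem.

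All of this stands, and it keeps the point minor. It does not remove it. Under a permissive list, the decision to adjust could be made after the data are seen, and settling it now costs almost nothing.

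Three stronger readings are tempting, and the documents support none of them:
- A reader might infer that the treatment estimate itself is materially less precise without the term. With all 40 analysed it is not, because stratified allocation has already delivered that gain.
- Because (b) keeps only those reaching 120% MT, a reader might infer that gender balance is lost and the unadjusted test rejects too often. That depends on how reaching 120% MT differs by arm and gender. The documents give no such rates, and an excess can be shown only by inventing them.
- A reader might infer that a gender term repairs the selection on tolerance. It can remove only a gender component of that selection, so no reduction in bias is claimed.

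**Conclusion.** The point holds as a minor one. Comparison (b) does not use the factor by which the trial randomises. If gender predicts VAS, its reported standard error is overstated, its interval is too wide and, with all 40 analysed, its test is conservative.

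Over assumed gaps of 0 to 0.8 SD, the unadjusted interval runs from 0.1% narrower to 7.5% wider with 40 analysed, and from 1.3% narrower to about 6% wider with about 24. If gender has no effect on VAS, the plain comparison loses nothing. These figures rest on normal scores, 60% women and an analysed subset that is random with respect to VAS. Confidence is medium, because the size of any gender effect is unknown.

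**What to change.** In SAP 6.6.2(b), state in advance that each subject's ramp-phase mean VAS will be analysed in a linear model with treatment and gender, and that the treatment coefficient will be reported with its confidence interval. The unadjusted comparison can be kept as a sensitivity analysis.

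The cost is one sentence and one degree of freedom; gender is already known at randomisation. If gender has no effect, the interval is wider by about 0.1% with 40 analysed, 0.6% with about 32 and 1.3% with about 24.

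A gender-stratified rank-sum (van Elteren) test for the nonparametric fallback is optional, because it is a trade-off. With no gender effect its power is 0.770 against 0.781 for the plain rank-sum test with 40 analysed, and 0.544 against 0.568 with about 24. It breaks even near a gap of 0.4 to 0.5 SD.

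The restriction of (b) to subjects reaching 120% MT needs separate treatment.
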